4.2 Study Schema

Note: refer to Dosing and Administration (Section 5.1.1) for further details on treatment scenarios.

Clinical Study Protocol RG1718030
Drug Substance: Nivolumab and Ipilimumab
IND Number:140818
Protocol version 3.0 April 17, 2019

Both ipilimumab and nivolumab are FDA approved, and the safety profile of both agents have been extensively studied. However, because the combination with radiation has not been previously studied, the first 6 patients of this study will represent the initial run-in phase of the triplet combination of nivolumab, ipilimumab and palliative radiation. The initial doses of ipilimumab and nivolumab will be administered on day 1 of therapy.

Stereotactic radiation will be initiated on Week 3 of treatment. SBRT will be delivered to a total dose of 24 Gy, given in 3 fractions of 8Gy every other day. Treatment will be continued according to the study schema unless patient withdraws consent, has confirmed disease progression, and/or develops toxicity that results in treatment discontinuation.

Enrollment will be halted until these first 6 patients complete the first 12 weeks of treatment and acute toxicities will be reviewed. If more than 2 DLTs (to be defined in Section 5.1.2) are noted in this six patient cohort, a dose modification will be implemented (Section 5.1.1) for the remaining 14 patients who will be enrolled in the expansion cohort.

Serum correlative studies will be collected at the following timepoints: at baseline, prior to week 8, and prior to week 16 of treatment. Archived formalin fixed paraffin embedded tissue (obtained in the 12 months prior to trial enrollment) will be collected from patients enrolled. If the patient does not have archived tissue available, a fresh biopsy will be obtained. Tissue requirement will be waived if deemed contraindicated or not clinically available/accessible for resection per the treating physician (PI approval required).

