5.1.2 Definition of DLT

Dose-limiting toxicities (DLTs) will be evaluated during the run-in phase consisting of the first 6 patients enrolled in this trial. The period for evaluating DLTs will be from the time of first administration of nivolumab and ipilimumab until 12 weeks. Adverse event monitoring will continue for these subjects throughout the course of their treatment as outlined in the Schedule of Study Assessments, these adverse events will include potential XRT related toxicities. Subjects who do not remain on the study up to this time for reasons other than DLT will be replaced with another subject. Grading of DLTs will follow the guidelines provided in the Common Terminology Criteria for Adverse Events (CTCAE) version 5.0.

A DLT will be defined as any Grade 3 or higher toxicity that occurs during the DLT evaluation period. Toxicity that is clearly and directly related to the primary disease or to another etiology is excluded from this definition. The following will be DLTs:

- Any Grade 4 irAE
- Any \geq Grade 3 colitis
- Any Grade 3 or 4 noninfectious pneumonitis irrespective of duration

- Any Grade 2 pneumonitis that does not resolve to \leq Grade 1 within 3 days of the initiation of maximal supportive care
- Any Grade 3 irAE, excluding colitis or pneumonitis, that does not downgrade to Grade 2 within 3 days after onset of the event despite optimal medical management including systemic corticosteroids or does not downgrade to \leq Grade 1 or baseline within 14 days
- Liver transaminase elevation $> 8 \times$ ULN or total bilirubin $> 5 \times$ ULN
- Any \geq Grade 3 non-irAE, except for the exclusions listed below
 - Grade 3 fatigue lasting \leq 7 days
 - Grade 3 endocrine disorder (thyroid, pituitary, and/or adrenal insufficiency) that is managed with or without systemic corticosteroid therapy and/or hormone replacement therapy and the subject is asymptomatic
 - Grade 3 inflammatory reaction attributed to a local antitumor response (e.g., inflammatory reaction at sites of metastatic disease, lymph nodes, etc.)
 - Concurrent vitiligo or alopecia of any AE grade
 - Grade 3 infusion-related reaction (first occurrence and in the absence of steroid prophylaxis) that resolves within 6 hours with appropriate clinical management

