 - Grade 3 or 4 neutropenia that is not associated with fever or systemic infection that improves by at least 1 grade within 3 days. Grade 3 or Grade 4 febrile neutropenia will be a DLT regardless of duration or reversibility
 - Grade 3 or 4 lymphopenia
 - Grade 3 thrombocytopenia that is not associated with clinically significant bleeding that requires medical intervention, and improves by at least 1 grade within 3 days
 - Isolated Grade 3 electrolyte abnormalities that are not associated with clinical signs or symptoms and are reversed with appropriate maximal medical intervention within 3 days
- Grade 4 hematologic toxicity, not described in exclusions above
- Prolonged delay (>2 weeks) in initiating second dose of nivolumab or ipilimumab due to treatment-related toxicity
- Grade 5 toxicity, i.e., death

Dose modification/delays according to Section 5.1.3 will apply to the patients who experience DLTs in the run-in phase.

Immune-related AEs are defined as AEs of an immune nature (i.e., inflammatory) in the absence of a clear alternative etiology. In the absence of a clinically significant abnormality, repeat laboratory testing will be conducted to confirm significant laboratory findings prior to designation as a DLT.

During this DLT period, patients who received <90% of the nivolumab OR ipilimumab infusion on day 1 (e.g., because the infusion of either drug had to be discontinued due to an infusion reaction) and did not experience a DLT will not be taken into account in the assessment of the overall DLT rate for the phase I run-in cohort and will be replaced.

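### The run-in's DLT-evaluability rules require no SBRT exposure, so a DLT-free patient with missing or incomplete SBRT still counts among the six who test the triplet

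*Combined protocol and SAP*

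**What the plan says.** Section 4.2 (Study Schema) gives the purpose of the run-in: "the first 6 patients of this study will represent the initial run-in phase of the triplet combination of nivolumab, ipilimumab and palliative radiation". The reason stated there is that both drugs have been studied extensively but their use with radiation has not. The same section sets the radiation schedule: "Stereotactic radiation will be initiated on Week 3 of treatment" and "SBRT will be delivered to a total dose of 24 Gy, given in 3 fractions of 8Gy every other day".

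Section 5.1.2 defines the observation window from the drugs, not from radiation: "The period for evaluating DLTs will be from the time of first administration of nivolumab and ipilimumab until 12 weeks". It then gives two replacement rules:

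- Early departure: "Subjects who do not remain on the study up to this time for reasons other than DLT will be replaced with another subject".
- Minimum exposure: "patients who received <90% of the nivolumab OR ipilimumab infusion on day 1" and who had no DLT are left out of the DLT rate and replaced.

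No DLT criterion in 5.1.2 refers to delayed or omitted SBRT. The one delay-type criterion is a delay of more than 2 weeks in the second dose of nivolumab or ipilimumab because of treatment-related toxicity.

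The run-in count selects the schedule for the remaining 14 patients. Section 5.1.1 acts at 2 or more DLTs; the Synopsis (Study Design) and section 4.2 act at more than 2. That conflict is a separate matter and must be reconciled. Both thresholds are carried below.

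**The concern.** The plan recognises that a DLT-free patient is informative only if exposed to the treatment, and it writes an exposure rule. That rule covers the two components described as well characterised and omits the one that motivates the run-in. A day-1 check cannot capture a component that starts in week 3.

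Followed as written, a patient who receives both day-1 infusions, then 0, 1 or 2 of the 3 fractions, stays on study to week 12 and has no DLT meets every condition for being counted. That patient says little or nothing about adding radiation, yet enters the count as a success for the triplet. If radiation adds DLTs, the count is biased downward and the unmodified schedule is more likely to go forward to the next 14 patients. With six patients, one or two such cases can matter.

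**Working it through.** **Step 1: read the rules against each case (no DLT observed).**

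| Run-in patient | Early-departure rule | Day-1 infusion rule | Result |
|---|---|---|---|
| Leaves study before week 12, not for DLT | applies | – | replaced |
| Under 90% of a day-1 infusion | – | applies | replaced |
| Full day-1 drugs, full SBRT, on study to week 12 | no | no | counted |
| Full day-1 drugs, no or partial SBRT, on study to week 12 | no | no | counted |

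The last row is the gap. It does not depend on any assumed rate.

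**Step 2: size.** The documents give no operating characteristics for the run-in, so there is no stated figure to reproduce. Let k be the number of the six without SBRT, pT the DLT probability with SBRT and pD the probability on the drugs alone. Assume independent patients and at most one counted DLT per patient. Then the number of DLTs is

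X = Bin(6 − k, pT) + Bin(k, pD).

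The rates are assumptions: pT = 40%, pD = 10%, 20% or 30%.

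*k = 0:* P(X ≤ 1) = 0.6⁶ + 6 × 0.4 × 0.6⁵ = 0.0467 + 0.1866 = 0.233, so P(X ≥ 2) = 76.7%.

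*k = 1, pD = 10%:* P(X = 0) = 0.6⁵ × 0.9 = 0.0700. P(X = 1) = 5 × 0.4 × 0.6⁴ × 0.9 + 0.6⁵ × 0.1 = 0.2411. The sum is 0.311, so P(X ≥ 2) = 68.9%.

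*k = 2, pD = 10%:* P(X = 0) = 0.1296 × 0.81 = 0.1050. P(X = 1) = 0.3456 × 0.81 + 0.1296 × 0.18 = 0.3033. The sum is 0.408, so P(X ≥ 2) = 59.2%. Adding P(X = 2) = 0.3456 × 0.81 + 0.3456 × 0.18 + 0.1296 × 0.01 = 0.3434 gives 0.752, so P(X ≥ 3) = 24.8%.

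All results at pT = 40%:

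| Patients without SBRT | pD | P(2 or more DLTs) | P(3 or more DLTs) |
|---|---|---|---|
| 0 | – | 76.7% | 45.6% |
| 1 | 10% | 68.9% | 35.2% |
| 1 | 20% | 71.5% | 38.7% |
| 1 | 30% | 74.1% | 42.1% |
| 2 | 10% | 59.2% | 24.8% |
| 2 | 20% | 65.4% | 31.7% |
| 2 | 30% | 71.3% | 38.7% |

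**Step 3: sensitivity.** With pT = 50% and pD = 20%, P(2 or more) is 89.1%, 84.4% and 78.0% for k = 0, 1 and 2; P(3 or more) is 65.6%, 56.2% and 45.7%. If pD = pT there is no bias. A patient with one or two fractions is given the drug-only rate here; a rate between pD and pT would make the effect smaller.

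**The case against.** **Omission should be uncommon.** Radiation evaluation and planning/simulation are scheduled at screening (sections 7 and 7.1.4.1). Inclusion criteria 5 and 6 require lesions suitable for SBRT and a patient able to tolerate the procedures. A plan that cannot meet its constraints, or a patient who cannot hold position, should usually be found before day 1. This stands. Nothing in the documents suggests that one or two of six would miss SBRT, so those cases are illustrations, not expectations.

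**Toxicity that cancels SBRT is often a DLT already.** A reader might infer that SBRT missed because of drug toxicity escapes the DLT definition. The documents do not support that. Nivolumab is given every 2 weeks, so its second dose falls in week 3, when SBRT starts, and a toxicity delay of that dose beyond 2 weeks is a DLT. So are Grade 4 immune-related events, Grade 3 or higher colitis, Grade 3 or 4 pneumonitis, persistent Grade 3 immune-related events and most other Grade 3 or higher toxicity. What remains is SBRT omitted for non-toxicity reasons, or for toxicity that meets no DLT criterion.

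**The text implies SBRT.** Section 4.1 says every patient is to receive all three components, and section 4.2 holds enrolment until six have completed 12 weeks of treatment. These statements describe planned treatment. They do not make SBRT a condition for being counted, and the explicit exposure rule names only the drugs. This softens the gap without closing it.

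**The drug-only rate drives the size.** The nearest figures in the sample size section are 28% treatment-related serious adverse events for the two drugs and a 30% design rate for Grade 3 or higher toxicity. Neither is a DLT rate, but both sit at the upper end of the assumed range. At pD = 28% and pT = 40%, P(2 or more) is 76.7%, 73.6% and 70.1% for zero, one and two patients without SBRT. The larger losses need a drug-only rate near 10%.

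**There are other safeguards.** The section 8.4 stopping rule covers drug-related Grade 4 or higher events throughout treatment, and all enrolled patients enter the safety analysis. Both limit the consequence; neither corrects the run-in count.

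**Conclusion.** The gap is real and rests on the text alone: section 5.1.2 has a minimum-exposure rule for the two drugs on day 1 and none for SBRT. The bias is downward if radiation adds DLTs and zero if it does not.

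Under the assumed rates (triplet 40%, drugs alone 10% to 30%), one patient without SBRT lowers the chance of 2 or more DLTs from 77% to 69-74%, and two lower it to 59-71%. For 3 or more, the fall is from 46% to 35-42% and to 25-39%. How often SBRT would be missed is not given and is probably low.

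A reader might infer that the run-in is likely to clear the triplet on patients who received only the drugs. The wording does not bar it, but the screening steps and the breadth of the DLT definition make it improbable. The point should be corrected in the protocol; it ranks below a defect that must be fixed before the trial can be relied on.

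**What to change.** Amend the evaluability text in section 5.1.2 as follows:

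1. A run-in patient without a DLT counts in the six only if, besides the existing conditions, they received the protocol SBRT course. The sponsor should state the minimum SBRT exposure required for evaluability. It should first reconcile the SBRT period, which is 1 week in the Synopsis and 2 weeks in footnote g of the Schedule of Assessments.
2. A patient without a DLT who does not meet this is replaced for the run-in decision but stays in the overall safety analysis.
3. A patient with a DLT always counts, whatever SBRT was given.
4. State in advance how a patient whose SBRT was omitted for treatment-related toxicity below the DLT criteria enters the run-in decision, so that the denominator is defined and such patients are not silently replaced.

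The cost is an occasional replacement: recruitment time in a rare disease at one centre, plus 12 weeks of follow-up, and one of the 20 places.

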5.1.3 Dose Delays/Modifications

Toxicity will be graded using Common Terminology Criteria for Adverse Events (CTCAE version 5.0). The protocol will change to CTCAE version 6.0 if is published within the course of the trial.

Because the toxicities of both nivolumab and ipilimumab overlap, a patient meeting dose delay criteria within weeks 1- 24 will have ***both nivolumab and ipilimumab held until improvement of the adverse event to Grade 1 or baseline and retreatment criteria are met.***

Nivolumab may be delayed until the next planned ipilimumab if the next ipilimumab dose is scheduled within the next 12 days. This will permit periodic ipilimumab or ipilimumab-placebo dosing to be synchronized with nivolumab dosing.

Ipilimumab should be dosed at the specified interval regardless of any delays in intervening nivolumab doses. However, in order to maintain periodic synchronized dosing of ipilimumab and nivolumab, the dosing days of nivolumab and ipilimumab-may be adjusted within the permitted -2/+3 day window, as long as ***consecutive nivolumab doses are given at least 12 days apart.*** Ipilimumab may be delayed beyond the -2/+3 day window if needed to synchronize with the next nivolumab dose

5.1.3.1 Dose Delay Criteria

Doses of both nivolumab and ipilimumab (during study weeks 1-24) or nivolumab alone (during study weeks 25-52) should be held if any of the following are observed:

- Any Grade ≥ 3 non-skin, drug-related adverse event, except for fatigue and laboratory abnormalities

- Any Grade ≥ 3 drug-related laboratory abnormality with the following exceptions for lymphopenia, aspartate aminotransferase (AST), alanine aminotransferase (ALT), or total bilirubin or asymptomatic amylase or lipase:
 - Grade 3 lymphopenia does not require a dose delay
 - If a subject has a baseline AST, ALT, or total bilirubin that is within normal limits, delay dosing for drug-related Grade 2 toxicity
 - If a subject has baseline AST, ALT, or total bilirubin within the Grade 1 toxicity range, delay dosing for drug-related Grade ≥ 3 toxicity
 - Any Grade ≥ 3 drug-related amylase or lipase abnormality that is not associated with symptoms or clinical manifestations of pancreatitis does not require dose delay.
- Any AE, laboratory abnormality or inter-current illness which, in the judgment of the investigator, warrants delaying the dose of study medication.

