5.1.3.2 Criteria for Resuming Treatment

Subjects may resume treatment with nivolumab and ipilimumab (weeks 1-24) or nivolumab (weeks 2-52) when drug-related AE(s) resolve(s) to Grade 1 or baseline value, with the following exceptions:

- Subjects may resume treatment in the presence of Grade 2 fatigue.
- Subjects who have not experienced a Grade 3 drug-related skin AE may resume treatment in the presence of Grade 2 skin toxicity.
- Subjects with baseline Grade 1 AST/ALT or total bilirubin who require dose delays for reasons other than a 2-grade shift in AST/ALT or total bilirubin may resume treatment in the presence of Grade 2 AST/ALT or total bilirubin.
- Drug-related pulmonary toxicity, diarrhea, or colitis must have resolved to baseline before treatment is resumed.
- Subjects who received systemic corticosteroids for management of any drug-related toxicity must be off corticosteroids or have tapered down to an equivalent dose of prednisone ≤ 10 mg/day.
- Drug-related endocrinopathies adequately controlled with only physiologic hormone replacement may resume treatment.

During weeks 1-24, ipilimumab may not be resumed sooner than 6 weeks (-2/+3 days) after the prior dose. In general, it should be feasible to synchronize dosing of both nivolumab and ipilimumab drugs when resuming treatment. In order to facilitate this, the dosing days of nivolumab and ipilimumab may be adjusted within the permitted -2/+3day window, **as long as consecutive nivolumab doses are given at least 12 days apart.**

If an ipilimumab dose is delayed beyond 6 weeks from the prior ipilimumab dose, then subsequent ipilimumab doses should be rescheduled to maintain the 6 week interval between consecutive ipilimumab.

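### Section 5.1.3.1 has no fixed dose hold for severe skin toxicity or for Grade 2 pneumonitis, so both rest on investigator judgment

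*Combined protocol and SAP*

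**What the plan says.** Section 5.1.3.1 lists when both drugs (weeks 1-24) or nivolumab alone (weeks 25-52) should be held. The line for clinical events reads "Any Grade ≥ 3 non-skin, drug-related adverse event, except for fatigue and laboratory abnormalities". A second line covers Grade 3 or higher laboratory abnormalities, with listed exceptions. One of these sets a lower threshold: if AST, ALT or bilirubin was normal at baseline, "delay dosing for drug-related Grade 2 toxicity". The last line is discretionary: "Any AE, laboratory abnormality or inter-current illness which, in the judgment of the investigator, warrants delaying the dose of study medication".

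Section 5.1.3 makes the consequence depend on that list: "a patient meeting dose delay criteria within weeks 1- 24 will have" both drugs withheld until the event has improved to Grade 1 or baseline and the retreatment criteria are met.

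Section 5.1.2 defines dose-limiting toxicity for the first 6 patients, over 12 weeks. Its list includes:

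- "Any Grade 4 irAE", with no exception for skin;
- "Any Grade 3 irAE, excluding colitis or pneumonitis, that does not downgrade to Grade 2 within 3 days after onset of the event" despite optimal management, or that has not reached Grade 1 or baseline within 14 days;
- "Any Grade 2 pneumonitis that does not resolve to" Grade 1 or lower within 3 days of starting maximal supportive care.

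The only skin conditions excluded from the DLT list are vitiligo and alopecia.

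Section 5.1.3.2 has a skin rule for restarting: "Subjects who have not experienced a Grade 3 drug-related skin AE may resume treatment in the presence of Grade 2 skin toxicity". It also requires drug-related pulmonary toxicity to return to baseline before restarting.

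**The concern.** The clinical hold line removes skin entirely, at Grade 4 as well as Grade 3, and starts at Grade 3 for everything else. Some events that the protocol itself treats as dose-limiting in the run-in therefore meet no written hold criterion except the investigator's own judgment.

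What is at stake is the next infusion for a patient with an unresolved serious skin reaction or lung inflammation. Pneumonitis is foreseeable in this trial. Up to 5 lung or bone lesions may be irradiated (Section 4.4), SBRT starts in Week 3 while both drugs are being given, and Section 4.2 says the combination with radiation has not been studied before.

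**Working it through.** No calculation applies. The check compares the rules event by event.

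| Event (drug-related) | DLT in run-in (5.1.2) | Fixed hold (5.1.3.1) | Rule for restarting (5.1.3.2) |
|---|---|---|---|
| Grade 4 skin irAE | Yes | No | General rule: Grade 1 or baseline |
| Grade 3 skin irAE, not downgrading in time | Yes | No | General rule, since a Grade 3 skin event removes the Grade 2 allowance |
| Grade 2 pneumonitis, not resolving in 3 days | Yes | No | Return to baseline |
| Grade 3-4 pneumonitis | Yes | Yes | Return to baseline |
| Grade 3 fatigue beyond 7 days | Yes | No, expressly exempt | Grade 2 fatigue allowed |

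The table leaves aside a Grade 3 skin irAE that downgrades promptly. It falls outside the listed DLT items, although the opening sentence of Section 5.1.2 is broader.

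**Do other sections supply the hold?**

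1. Sections 5.1.1 and 5.1.2 both say that run-in patients with a DLT will have their dosing interrupted or modified, but both take the content from Section 5.1.3. Following the reference leads back to a list with no trigger for the first three rows. The 14 expansion patients have no such reference.
2. The holding rule in Section 5.1.3 applies only once a dose delay criterion is met.
3. Section 5.1.3.2 governs restarting, so it operates only after dosing has stopped.
4. Section 5.1.3.3 has no discontinuation rule specific to skin or pneumonitis. Its adverse event clause depends on the opinion of the investigator or sponsor.
5. Under Section 8.4, a Grade 4 drug-related skin event counts toward halting enrolment (more than 3 patients with such toxicity). That rule does not address the affected patient's own next dose.

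**Can the event be present when a dose is due?** Yes. In the run-in, the pneumonitis item and the first branch of the Grade 3 irAE item can be met after 3 days. Nivolumab is planned every 14 days in weeks 1-24 and never less than 12 days apart. A patient can therefore already have a DLT of this kind at the next dosing visit with no written rule stopping the infusion.

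**Was a hold intended?** The skin rule in Section 5.1.3.2 makes a prior Grade 3 skin event a bar to restarting at Grade 2. That condition is most natural if a Grade 3 skin event interrupts dosing. The pulmonary rule says less, because it is needed anyway for Grade 3 or higher pneumonitis, which does have a fixed hold. The Grade 2 liver line shows only that a Grade 2 trigger is not foreign to this plan.

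**The case against.** The strongest reply is that DLT criteria and hold criteria do different jobs. The first set the dose for the expansion cohort and the second manage individual patients, so they need not agree. Fatigue shows this: Grade 3 fatigue beyond 7 days is a DLT, is exempt from the hold on purpose, and still has a restarting line. This stands. A reader might infer that every DLT without a fixed hold is an error, or that a line in Section 5.1.3.2 proves a hold was meant. The fatigue lines rule out both inferences. The restarting lines can also serve patients held for another reason who have a concurrent rash or fatigue.

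The reply also has force on practical risk. The judgment line is itself a listed criterion, so invoking it brings the full hold into effect. Adverse events are reviewed at each dosing visit and the team meets weekly. Patients with interstitial lung disease or pneumonitis are excluded, as are SBRT targets within 2 cm of the proximal bronchial tree, and Section 5.2.3 sets lung dose limits. The run-in wording signals that a DLT should lead to interruption. All of this makes an inappropriate infusion less likely, but none of it requires a hold.

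A further reading to avoid is that DLT categories lack a hold for all 20 patients throughout treatment. DLTs are assessed only in the first 6 patients and only to week 12. Beyond that, what applies to everyone is the absence of a fixed hold, without the DLT label.

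**Conclusion.** The point holds as a patient-safety gap in the written rules. Drug-related skin events of any grade and Grade 2 pneumonitis have no fixed hold, in the run-in or the expansion, and depend on investigator judgment. The skin part is the stronger one: Grade 4 is exempt along with milder grades, and the restarting rule suggests, without proving, that a Grade 3 skin hold was intended. For pneumonitis the argument is clinical: a listed DLT, possible lung irradiation and two checkpoint inhibitors given together.

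The size cannot be put as a number. The documents give no rate for these events, and even an assumed rate would give the chance of an event, not of an inappropriate dose. The documents do not show that any patient would in fact be treated through such toxicity.

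A reader might also infer damage to the trial's statistics. That is not supported: events are recorded and graded whether or not a dose is held, so the sample size reasoning and the run-in decision stand. The conclusion rests on a literal reading of Section 5.1.3.1 and on taking the judgment line as discretionary.

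**What to change.** Add two lines to Section 5.1.3.1:

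- *Any Grade ≥3 drug-related skin adverse event*
- *Any Grade ≥2 drug-related pneumonitis*

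Each holds both drugs in weeks 1-24 and nivolumab in weeks 25-52. Section 5.1.3.2 already says how to restart after skin and pulmonary toxicity, so it needs no new wording. The fatigue and asymptomatic amylase or lipase exemptions can stay as they are.

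The cost is a short amendment, with no added procedures, data or patients. Some doses will be delayed that an investigator would have given, including for Grade 3 skin events that would have downgraded quickly and Grade 2 pneumonitis that would have cleared within 3 days. One limit remains: causality in Section 8.2 is judged against study drug, so pneumonitis attributed to radiation alone would still rest on the judgment line.
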